The Effect of Tablet Size on Cognitive Performance:

A Randomized Control Trial Using Caffeine

[name]

University of Colorado Denver

[name]

[name]

[name]

July 9, 2018

Abstract

Background: A capsule's physical design (e.g. shape, size, and color) affects individuals' perception of drug efficacy; that is, how well a drug is likely to work. The goal of this study is to assess the effects tablet size may have on participant's performance on cognitive testing since research has found differences between preparation methods. **Method:** 120 participants will be randomly assigned to one of four groups: 1) 90 mg caffeine with a 1 mm diameter sucrose pillule; 2) no caffeine with the small sucrose pillule; 3) 90 mg caffeine with a 5 mm sucrose pillule; 4) no caffeine with the large sucrose pillule. Participants will consume the designated placebo tablet with water (caffeinated or non-caffeinated); then, participants will provide weekly caffeine intake and complete the neutral portion of Velten's Mood Induction Procedure until 30 minutes have passed to allow for caffeine activation. Participants will complete the Stroop test, Trial Making Tests A and B, and the Rey Auditory Verbal Learning Test. Previous literature, as far as the author knows, relied on evaluating drug efficacy based on appearance alone. This study aims to assess if tablet size, due to placebo effect, alters participants' performance on cognitive tests after consuming caffeinee. The Effect of Tablet Size on Cognitive Performance:

A Randomized Control Trial Using Caffeine

Placebo effects are physiological changes in the brain and body brought about through treatments that have no active ingredient or active component (Geuter et al., 2017). Historically, placebo effects have been utilized as a marketing tool because the public's beliefs, expectations, experiences, and perceptions made the proposed treatments and products appealing. For example, in the 1700s, Franz Anton Mesmer developed his theory of "animal magnetism" (Hammond, 2013). His theory asserted "mesmeric" (i.e. hypnotic) motions over a patient's body would redistribute and realign magnetic fluids within the body, curing clients of their ailments. However, after much criticism, Mesmer's claim was found to be unsupported by experimental evaluation. His peers concluded that the results from his treatments were more likely due to his clients' imaginations than his theory on animal magnetism (Hammond, 2013). In other words, Mesmer took advantage of his clients' susceptibility to mesmerism, or hypnotism, to create a physiological response during treatment.

There are different methods to elicit a physiological response in individuals using placebos. Pseudo-pharmaceutical placebos include mixtures created from Galen's Pharmacopeia, a recipe book that uses plants, bacteria, worms, reptiles, fish, human organs, tissue, bone powder, or excretion to create "medicinal remedies." Before the 19th century, this recipe book was believed to provide cure all recipes for ailments (Czerniak & Davidson, 2012). If the patient died, then the ailment was incurable, and no remedy would have worked. Why have placebos endured throughout history? Literature suggests that one explanation could be how individuals perform perceptual decision making (Geuter et al., 2017).

3

Bayesian models of perceptual decision making suggest that creating biased perceptions in favor of expected values or outcomes results in outcomes that fulfill those expectations. For example, if an individual expects pain, introducing a placebo may create the expectation of experiencing less pain. If the placebo is successful, the individual will experience an analgesic effect without any active ingredient. These placebos can be applied in many different situations, where an individual's perceptions or expectations influence the outcome of their treatment or intervention.

In recent research, a placebo effect may have been responsible for differences in participant responses to experimental procedures. Initially, the placebo effect threatened the validity of previous research, because its effects were not well understood (Ross & Buckalew, 1979) among the different scientific disciplines. The placebo effect in scientific literature was still an unintentional and unexplained effect; psychological and behavioral changes were observed in different studies repeatedly (Buckalew, 1979). As more evidence surfaced, the demand to better understand the placebo effect increased. Understanding the placebo effect would not only safeguard and improve research quality; the placebo effect showed promise to be manipulated to explore possible beneficial uses.

Physical drug design

Research since then suggests that the physical design of drugs influences an individual's perception of a drug. Specifically, the color, shape, size and coating of the drug have been found to impact preferences, how strong an individual perceives a drug to be and the effect they believe a drug will have (e.g. tranquilizer, stimulant, etc.; Buckalew & Coffield, 1982).

4

Buckalew and Coffield's research on the effects of capsule size on perceived drug strength suggests that larger capsules are believed to be stronger than small capsules (Buckalew & Coffield, 1982). In their study, college students were recruited to assess the relationship between perceptual characteristics of physical drug preparation forms (i.e. formulation) and expected effects. The influence of capsule size on perceived drug strength, the influences of color on expected drug effects, and the influence of formulation on expected drug strength were all visually assessed. Their findings suggest that certain colors are related to expected pharmacological effects. Furthermore, capsules are perceived to be stronger than tablets, and capsule size is significantly related to expected drug strength. Larger capsules are perceived to be stronger compared to smaller capsules. In tablets, the same pattern might persist; however, the opposite effect might also occur. Smaller tablet sizes might result in a stronger effect than larger tablet sizes. Buckalew and Coffield's work relied on visual judgements of drug characteristics; however, this study will rely on quantitative data to evaluate tablet size's effects on participants' performances due to participant perception.

Overgaard et al.'s study aimed to assess the preferences of oral dosage forms by size, formulation (i.e. gelatin capsule, tablet, or coated tablet), and shape (Overgaard et al., 2001). The study was designed in three phases, each assessing one of the previously mentioned factors. To assess how size affects swallowability and preference, participants were each asked to swallow five differently sized oblong tablets and verbally rate how easily they were able to swallow each pill according to a 5-point Likert scale. Smaller tablets were found easier to swallow compared to larger ones. To assess what formulation is preferred, participants were asked to swallow a gelatin capsule, tablet, and coated tablet and rate which was easier to

swallow. Gelatin capsules were easiest to swallow, followed by coated tablets and non-coated tablets. Lastly, to assess the preferable shape participants were asked to visually judge small, medium, and large white tablets that were circular or oblong on swallowability. Medium and large tablets were rated the easiest to swallow if they were oblong, while small tablets were rated easiest to swallow when they were round (Overgaard et al., 2001). Overgaard et al.'s work established preferences for physical drug designs. However, little is known if those physical characteristics can influence the placebo effect influencing the performance of the drug. This study will focus on one size, specifically in tablets, to assess if that characteristic can affect cognitive outcomes in a quantifiable manner. Despite extensive library searches, no research was found that analyzed tablet-based, physical design factors, like size, that could influence a placebo effect and consequently drug performance.

Caffeine

Caffeine is a psychostimulant with three main mechanisms ofaction : 1) mobilization of intracellular calcium, 2) inhibition of phosphodiesterases, and 3) antagonism of adenosine receptors (Nehlig et al., 1992). Caffeine stimulates the release and reuptake of calcium in neurons and muscle-tissue cells; an essential process in the central and peripheral nervous systems for neuronal communication and muscle contraction in the musculoskeletal system. Caffeine inhibits the breakdown of phosphodiesterases in the central nervous system. Caffeine's molecular structure is like that of enzymes responsible for breaking down phosphodiesterases into molecules like cAMP, a messenger molecule. This action, though, occurs when there is a toxic concentration of caffeine in the blood. The mechanism of action associated with improving cognition after consuming caffeine is the antagonism of adenosine

6

receptors. Adenosine is responsible for dampening neuronal activity in the suprachiasmic nucleus (e.g. less electrical activity, less neurotransmitter release, etc.). The physiological response associated with uninhibited adenosine receptors (i.e. with no caffeine present) is feeling drowsy, sleepy, and less attentive. Caffeine has a high affinity for adenosine receptors (specifically the A₁ receptor), so adenosine receptors are blocked by caffeine molecules (Nehlig et al., 1992). Consequently, individuals can experience the opposite physiological response: better attention, feeling awake, improved attentiveness, etc. The consequences of caffeine's third mechanism of action have been thoroughly researched, making it a strong drug candidate for use in this study.

Caffeine may be a good option for testing this phenomenon for three reasons: 1) previous research already supports caffeine's improvements to cognitive functioning (EFSA, 2011); 2) caffeine use among college students is very salient, given the prominence of the caffeine across various products like energy drinks (Pettit & DeBarr, 2011); 3) using self-report measures to collect data on weekly caffeine consumption habits will allow adjustments for tolerance effects (Beaumont, et al., 2017;2016). Research on caffeine use in healthy adults has already shown significant improvement to memory, executive functioning, and processing speed (EFSA, 2011). Caffeine lends itself well to a randomized controlled trial design, allowing the introduction of tablet size as an additional factor. Previous research supports an increase in cognitive functioning after consuming caffeine; memory, executive functioning, and processing speed are improved after consuming caffeine (EFSA, 2011). The European Food and Safety Administration conducted a meta-analysis that assessed the different claims associated with consuming caffeine like increased fat oxidation, increased energy expenditure, increased

alertness, and increased attention. Their findings suggest that there is not enough data to support causal claims for caffeine causing increased fat oxidation and increased energy expenditure. However, a causal relationship between caffeine and increased alertness and increased attention is supported (EFSA, 2011). Pettit and Debarr conducted a study analyzing the association between stress and energy drink consumption, and the association between energy drink consumption and GPA in 136 college students ages 18-24 (Pettit & DeBarr, 2011). Their results show a positive correlation between perceived stress and energy drink consumption, and a negative correlation between GPA and energy drink consumption. However, the results in Pettit and DeBarr's study did not account for consumption of caffeine from other sources (e.g. coffee, tea, supplements, etc.). Heavy marketing for caffeinated products make caffeine an ideal substance to use for assessments when working with college students.

Beaumont et al.'s research on tolerance development for low doses of caffeine emphasizes the need to adjust for tolerance effects in randomized controlled trials (Beaumont, et al., 2016; 2017;). Their research examined participant physical performance after consuming small doses of caffeine. Participants experienced significant decline in performance after consuming small doses of caffeine (1.5 mg of caffeine per kg of bodyweight) for 28 consecutive days compared to placebo. Beaumont et al.'s work highlights the importance of adjusting for participants' caffeine consumption habits. Leaving scores unadjusted for caffeine consumption habits could be a confound to studies that involve participants consuming caffeine.

Lastly, age is a significant factor in caffeine metabolism. Some hepatic enzymes (Cytochrome P450s, or CYPs) become less active as individuals age (Kinirons & O'Mahony,

8

2004). There are several different CYPs that metabolize different drugs. Caffeine is metabolized by CYPs in the 1A family, specifically 1A2 CYPs. Kinirons and O'Mahony's literature analysis showed consistent decrease in enzyme activity as individuals age (Kinirons & O'Mahony, 2004). They suggest the decreases in certain enzyme activity are likely due to changes in liver size and blood flow. Livers in humans experience a size reduction and reduced blood flow with age. When conducting research that involves participants metabolizing caffeine, age should be considered. Caffeine is a good choice to examine the effects tablet size may have on participants' performances on cognitive tests.

Present Study

Previous research relied heavily on participants' perceptions to rate a drug's effectiveness and purpose; this study was designed with randomized, placebo-controlled trials to evaluate the main goal using objective quantitative data. I will use neuropsychological testing to assess if tablet size affects participants' short-term memory, executive function, and processing speed using caffeine as the drug of choice. Previous research has supported a significant cognitive boost in these cognitive functions for caffeine dosages of at least 75 mg (EFSA, 2011). If tablet size affects perceptions of how effective a dose of caffeine will be, despite doses remaining constant in the caffeinated groups, then I expect significant differences among the two tablet sizes for processing speed, executive functioning, and memory capabilities in participants. This study may prove foundational to better understanding more effective physical drug designs.

Hypotheses

There are three hypotheses for this experiment:

- caffeine will significantly improve participant's memory, executive function, and processing speed;
- there will be a significant difference in participant performance associated with tablet size;
- 3) there will be an interaction effect between caffeine content and tablet size.

Method

Participants

120 participants, primarily Psychology students fulfilling a research participation requirement for Introduction to Psychology courses, will be recruited. Ambulatory participants that are fluent in written and spoken English will be used because they should be able to complete the neuropsychological tests.

Participants that are allergic to sucrose and/or caffeine will be excluded because they are essential components to the procedure. Participants with cardiovascular disease or uncontrolled high blood pressure will be excluded because the use of caffeine may exacerbate these conditions. Participants with untreated or unresolved anxiety and/or depressive disorders will be excluded because caffeine may exacerbate symptoms related to these disorders as well. Participants that are pregnant will be excluded from this study. Lastly, participants that have a diagnosed learning disability will be excluded because the neuropsychological tests will only use scores normalized for the general population.

Participants' age will be limited to ages 18 years old through 40 years old because age is a significant factor in caffeine metabolism (Kinirons & O'Mahony, 2004). Individuals older than 40 may experience different pharmacological effects due to age; thus, age will be controlled in this study.

Measures

Processing Speed.

Stroop 1) Color and 2) Word tests.

The Color test asks participants to read the color of print on a page with columns of red, yellow, green, and blue X s. The Word test asks participants to read the printed words on a page with the words RED, YELLOW, GREEN, and BLUE printed in black ink. These tests are scored by timing, in seconds, how long participants take to correctly identify the 100 items in each test. Longer completion times indicate slower processing speed capabilities. The Stroop Test's separate 1) Color and 2) Word tests (Appendix B) test-retest reliabilities are .83 and .74, respectively (Franzen, et al., 1987)

Trail Making Task A.

This test asks participants to connect a series of numbers that are randomly distributed on the test page. The goal of these tasks is to connect the series of numbers or numbers and letters in order (e.g. 1-2-3) as quickly as possible. Scoring is done by recording the time (in seconds) participants needed to complete the test. Longer completion times indicate slower processing speed capabilities. The Chronbach's alpha reliability of Trail A is .86 (Smith, et al., 2008).

Executive Function.

Stroop 3) Color-and-Word test.

The Color-and-Word test asks participants to read the color of print for the words RED, YELLOW, GREEN, and BLUE when the print color and word conflict. This test is scored by timing, in seconds, how long it takes for participants to correctly read 100 items. Longer completion times indicate lower executive function capabilities because the conflict between the print color and printed word takes longer to overcome. The test-retest reliability of the Stroop Colorand-Word Test is .67 (Franzen, et al., 1987).

Trail Making Task B.

This test asks participants to connect a series of numbers and letters that are randomly distributed on the test page. The goal of these tasks is to connect the series of numbers and letters in order (e.g. 1-A-2-B-3-C) as quickly as possible (Appendix C). Switching between alphabetic and numeric sets and timing completion times, in seconds, is an effective measure of executive functioning capabilities. Longer completion times indicate lower executive function capabilities because participants take longer to switch between sets. The Cronbach's alpha of Trail B is .88 (Smith, et al., 2008).

Memory.

Rey Auditory Verbal Learning Test (RAVLT).

Participants are presented with 15 unrelated words and asked to recall as many as they can over five trials. This section assesses immediate recall ability. An additional 15 unrelated words are then introduced as an interference component. Participants must recall as many of the original 15 words as possible after being presented with interference. Lastly, after an interval of 30 minutes, participants are asked to recall the original 15 words again (Appendix D). The trials are scored by counting the correct number of words recalled, the % recalled (the final delayed-recall trial(A7) divided by the final immediate recall trial (A5)), and the number of intrusions (i.e. the number of incorrect words). A higher percentage of recall with little to no intrusions are considered better memory. The Cronbach's alpha reliability of the Rey Auditory Verbal learning Test is .84 (Magalhaes, et al., 2012).

Procedure

Materials for this procedure will need to be prepared beforehand. 90 mg packets of caffeine will be prepared from 200 mg pure caffeine powder capsules by opening capsules and measuring out the desired weight of caffeine using a scale that can measure accurately to the thousandths gram. The weight of each prepared packet will be recorded by hand in a notebook until it is used in a trial. Before participants arrive, the prepared caffeine packet will be mixed with distilled water and one pillule of each size will be placed into small paper cups marked A and B.

Procedures will be explained to participants at first contact, and they will sign an informed consent form to confirm eligibility (Figure 2). Participants will be randomly assigned to one of the four groups (Figure 1). Based on a power analysis conducted at 0.80 power on Pasman et al.'s work on the effects of caffeine in a home-setting, 120 participants will need to be recruited in this study to successfully detect any significant effect (Pasman et al., 2017).

Participants will be required to not have consumed caffeine the day of testing. Participants will be presented with 8 ounces of distilled water and the cups containing each sucrose placebo pill. They will be asked to drink the water and only one of the sucrose pillules (depending on the group they were placed in); half of the participants (n=60) will drink water mixed with 90 mg of dissolved caffeine (Figure 1). After consumption, participants will be asked to complete Velten's Neutral Mood Induction Procedure (Appendix A) until 30 minutes have passed to allow for caffeine activation in the body (Institute of Medicine (US) Committee on Military Nutrition Research, 2001). Participants will then begin with the series of Stroop tests. After completing the three Stroop tests, participants will complete the first section of the Rey Auditory Verbal Learning test (immediate recall). During the 30-minute waiting period

participants will complete Trail Making Tasks A and B, and fill out a demographic survey designed to collect: 1) their weekly caffeine intake using the Caffeine Consumption Questionnaire (Appendix E); 2) sex; 3) age; 4) ethnicity and race; 5) year in school (i.e. freshman, sophomore, etc.); 6) GPA; and 7) academic major. The time of day the trial begins will also be recorded. The data collected in the survey will be used to adjust scores during data analyses. If students are unable to complete the survey and caffeine questionnaire within the 30-minute waiting period allotted for the RAVLT, the survey materials will be set aside and completed after participants finish the second component of the RAVLT. After completing the second portion of the RAVLT participants will be debriefed, and the trial will conclude.

Data Analysis

Primary analysis will be done through a series of ANCOVAs, if a preliminary correlation analysis shows a significant relationship between weekly caffeine consumption and scoring for each cognitive component. If the preliminary correlation analysis does not show a significant relationship between weekly caffeine consumption and scores for each cognitive component, then a series of ANOVAs will be performed.

Proposed Timeline

Pending the approval of clinicaltrials.gov, materials will be gathered and prepared in early October. The UROP has been awarded and funds will be available once PRS has approved of this proposal. Recruitment will begin during the Fall semester. Recruitment and trials are expected to continue in through December and conclude as late as February. Course load will be kept to a minimum to allot enough time for trials every weekday during the morning.

[figure not shown]
15

Weekly caffeine consumption will be calculated for each participant from their reported

caffeine consumption habits (Appendix E).

	No caffeine	90 mg caffeine
Small tablet (1 mm diameter)	Average score on cogitive test	Average score on cognitive test
Large tablet (5 mm diameter)	Average score on cognitive test	Average score on cognitive test

Figure 1. Overall study design

The Effect of Tablet Size on Cognitive Performance: A RCT Using Caffeine

Figure 2. CONSORT diagram

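### Colour vision is not screened although two Stroop scores depend on naming coloured print, which adds avoidable noise of uncertain, possibly small, size to those scores

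*Combined protocol and SAP*

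**What the plan says.** **Who is admitted.** Method, Participants: "Ambulatory participants that are fluent in written and spoken English will be used because they should be able to complete the neuropsychological tests." The exclusions that follow are allergy to sucrose or caffeine, cardiovascular disease or uncontrolled high blood pressure, untreated anxiety or depression, pregnancy, and diagnosed learning disability. An age limit of 18 to 40 comes after them. Colour vision is not listed. The Procedure describes no colour-vision check, and neither its list of survey items nor the survey in Appendix F asks about it.

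**What the tests require.** Measures, Processing Speed: "The Color test asks participants to read the color of print on a page with columns of red, yellow, green, and blue X s." Measures, Executive Function: for Color-and-Word, participants must "read the color of print for the words RED, YELLOW, GREEN, and BLUE when the print color and word conflict." The Word test is different, because its words are "printed in black ink." The Color and Word tests are scored in seconds, by "how long participants take to correctly identify the 100 items in each test". The Color-and-Word test is likewise timed over 100 correctly read items. Longer times are interpreted as slower processing or weaker executive function.

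**How the scores are used.** The Procedure places all testing after the dose, so there is no baseline Stroop score. Data Analysis names a series of ANCOVAs or ANOVAs, with weekly caffeine consumption as the only named covariate. No time cap, non-completion rule or outlier rule is given. The Stroop score sheet in Appendix B has a line for Color-Word errors, but nothing says how it enters the analysis.

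**The concern.** The plan's own reason for its fluency rule is that participants must be able to do the tests. Telling the four print colours apart is as basic to two of the Stroop sheets as reading English is to the rest of the battery. A participant who confuses some of the colours may hesitate and self-correct, which lengthens the time, or may make errors. Either way the score partly reflects colour vision and not the construct it is meant to measure.

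The analysis has nothing to absorb this. There is no baseline score to subtract, no colour-vision covariate and no rule for extreme times. The stake is precision on one processing-speed score and one executive-function score. There is also a smaller procedural risk: if an odd Stroop result is noticed during testing, the decision to keep or drop it would be made ad hoc.

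**Working it through.** **Inputs from the documents.** N = 120, with 60 on caffeine and 60 not, hence 30 per cell if the four groups are equal; power 0.80 (Procedure).

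**Inputs not in the documents, assumed here.** Alpha 0.05 two-sided. Share of participants affected, p: 0.5% to 8%. Mean slowing in those affected, k: 1 to 3 within-group SD. Errors are not modelled; the calculation treats the whole effect as lost time.

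**Step 1: the plan's own figure.** The 120 cannot be reproduced, because no effect size, SD, alpha or sidedness is stated. Working backwards, the standardised difference that 60 against 60 detects with 80% power is

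d = (1.960 + 0.842) × √(2/60) = 2.802 × 0.1826 = 0.511.

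This serves as the reference effect for a main effect of caffeine or tablet size.

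**Step 2: variance inflation.** If a share p is slowed by k SD, independently of arm, the within-group variance is multiplied by

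V = 1 + p(1 − p)k².

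Examples:
- p = 4%, k = 1: 1 + 0.0384 × 1 = 1.038
- p = 2%, k = 2: 1 + 0.0196 × 4 = 1.078
- p = 4%, k = 2: 1 + 0.0384 × 4 = 1.154
- p = 8%, k = 3: 1 + 0.0736 × 9 = 1.662

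**Step 3: power.** Power = Φ(2.802/√V − 1.960). For p = 4%, k = 2: √V = 1.074, so Φ(2.608 − 1.960) = Φ(0.648) = 0.742. The full grid, against 0.800 with no affected participants:

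| Share affected | Slowing 1 SD | 2 SD | 3 SD |
|---|---|---|---|
| 0.5% | 0.798 | 0.792 | 0.783 |
| 2% | 0.792 | 0.770 | 0.733 |
| 4% | 0.785 | 0.742 | 0.676 |
| 8% | 0.772 | 0.692 | 0.584 |

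The loss runs from 0.2 points (top left) to 21.6 points (bottom right).

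**Step 4: N needed to restore 80%.** This is 120 × V, rounded up to equal arms. At 2 SD slowing it is 130 for p = 2% (120 × 1.078 = 129.4) and 140 for p = 4% (120 × 1.154 = 138.4, or 69.2 per arm).

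**Step 5: chance of meeting the problem at all.** The probability of at least one affected participant is 1 − (1 − p)^120: 45% at p = 0.5%, 91% at 2% and 99% at 4%. The expected numbers are 0.6, 2.4 and 4.8 people.

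**Step 6: check by simulation.** A simulated 2 × 2 ANOVA with 20,000 runs per setting gave main-effect power of 0.793 with nobody affected, 0.740 at p = 4% and k = 2, and 0.581 at p = 8% and k = 3. Type I error stayed between 0.047 and 0.053 for both main effects and the interaction.

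**The case against.** **The mechanism is not established.** A reader might infer that a colour-deficient participant must record a very long time. The documents do not support that. The word correctly in the scoring rule could mean that every miss is put right on the clock, but the Appendix B sheet records Color-Word errors separately, so confusion may appear there and not in the time. The text does not settle which applies. This objection stands, and it is why slowing is treated as possible and the range starts at 1 SD.

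**The size rests wholly on assumptions.** This also stands. With prevalence of 0.5% or less, the loss is under 2 points even at 3 SD. The large losses need high prevalence and heavy slowing together.

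**Chance imbalance adds no separate harm.** A reader might worry that one or two extra affected people in an arm would distort the result. Two extra people slowed by 2 to 3 SD shift the mean of an arm of 60 by 4/60 to 6/60, that is 0.07 to 0.10 SD. The standard error of the arm difference is √(2/60) = 0.18 SD. The shift is ordinary chance variation, already counted in V.

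**Other measures remain.** Stroop Word and Trails A still inform processing speed, Trails B still informs executive function, and RAVLT is untouched. True, and it limits the consequence.

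**A check may exist elsewhere.** Eligibility is confirmed through the consent form and Figure 2, neither of which can be read in the available text. The exclusion list is not the only place where requirements appear, since the age limit and same-day caffeine abstinence come after it. A check there cannot be ruled out.

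**Conclusion.** The point holds as a minor, cheap improvement. In the text available, nothing screens for colour vision, and two timed scores depend on it. The effect is added noise on Stroop Color and Stroop Color-and-Word only. It does not bias the comparison of arms or raise the type I error.

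The direction of the loss is certain if anyone is affected and slowed; its size is not. Relative to 80% power for d = 0.511, and under the assumed alpha, prevalence and slowing, the loss is 0.2 to about 22 points. It is under 2 points at 1 SD with prevalence up to 4%, and about 3 to 6 points at 2 SD with prevalence of 2% to 4%.

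A reader might also infer that the learning-disability exclusion shows the plan screening twice for ability to complete the tests and then forgetting colour vision. It does not. That exclusion has a different reason: "Lastly, participants that have a diagnosed learning disability will be excluded because the neuropsychological tests will only use scores normalized for the general population." Only the ambulatory and fluency criterion carries the ability rationale, and that alone is enough for the point.

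**What to change.** 1. Add self-reported colour-vision deficiency to the exclusions in Method, Participants, and ask about it with the other eligibility questions before assignment. If the consent form or Figure 2 already contains such a question, repeat it in the Participants section.
2. State in Data Analysis that if a deficiency comes to light after assignment, the participant stays in the trial and only the Color and Color-and-Word scores are omitted. Fix the rule before arms are known, and make the trigger the participant's report of colour vision, not a long time or a high error count, so that the outcome does not decide its own inclusion. The Word score stays.
3. Say how the Color-Word errors line is used, if at all.

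**Cost.** One yes/no question. A few volunteers become ineligible and are replaced from the same student pool. Screening first is the cleaner route, because late omission without replacement itself costs a little: power 0.784 if 4% are dropped and 0.766 if 8% are. That is better than leaving them in at 2 SD slowing (0.742 and 0.692), but no better at 1 SD (0.785 and 0.772).
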